4.7.1.3 Reporting of SAEs

Investigators and other site personnel must inform appropriate AstraZeneca representatives of any SAE that occurs at his or her centre in the course of the study within 1 day (in this section, within 1 day is defined as “immediately but no later than the end of the next business day”) of

when he or she becomes aware of it (initial SAE report). This should apply whether or not the SAE is considered causally related to the investigational product or to the study procedure(s). Wherever possible, this report should be made following the “Reporting Procedure of SAEs using Web-based Data Capture (WBDC) system” described below. The principal investigator must provide detailed information to AstraZeneca in writing within 4 calendar days of the initial report. The principal investigator must notify the SAEs in writing to the head of the study site immediately.

Follow-up information on SAEs must also be reported to AstraZeneca by the investigator(s) within the same time frames. If a non-serious AE becomes serious, this and other relevant follow-up information must also be provided to AstraZeneca within 1 day as described above.

The following information is required in the initial SAE report to AstraZeneca from the investigator(s); study code, centre number, subject number, AE, seriousness, start date. The following detailed information must be sent to AstraZeneca within 1 day after it becomes available; severity, outcome (including stop date, if available), causality (investigational product and if applicable any other concomitant drug), date when a non-serious AE became serious, withdrawal of study treatment, treatment of AE, concurrent therapy (except for treatment of AE), concurrent medication (including pre-study medication if the causality of the AE cannot be assessed), date of birth, sex, other current illnesses, relevant medical history and if applicable, date and course of death.

If initial or the subsequent reports are made by means other than WBDC, necessary information on any SAEs should finally be entered into eCRF via WBDC system by the investigator(s).

For all SAEs, the AstraZeneca representative will inform the AstraZeneca Drug Safety Department of it by Day 1 and will work with the investigator(s) to compile all the necessary information and ensure that the Drug Safety Department receives a report within 4 calendar days.

In addition AstraZeneca will provide details of any unexpected serious adverse drug reactions or expected fatal or life-threatening serious adverse drug reactions reported with regard to the test product and the control drug if not unblinded in this study or other compound available overseas in which the active ingredient is known to be equivalent to the test product, to the head of the study site, principal investigator and the regulatory agency. The head of the study site must submit a written report to the IRB providing the details of all AE case(s) reported by AstraZeneca.

(a) Reporting Procedure of SAEs using WBDC system

The investigator(s) and other site personnel will access WBDC system and report SAE information by entering it into the relevant eCRF module. Upon entry of the SAE information, an automated email alert will be sent to the designated AstraZeneca representative.

If the system is unavailable, the investigator(s) should take other appropriate measures to provide SAE report to the AstraZeneca representative immediately, recognising that the same reporting time frames still apply. The investigator(s) is responsible for completing the eCRF as soon as the system becomes available again.

4.7.2 Laboratory safety measurements and variables

4.7.2.1 Test items

Laboratory tests are performed on Visits 1 (baseline), 3 and 4.

The test items are shown below. See [Table 8](#) for the collected amount of blood.

Table 7 The items of laboratory safety

	Items
Biochemistry test:	AST (GOT), ALT (GPT), γ -GTP, ALP, LDH, total bilirubin, total protein, albumin, BUN, creatinine, uric acid, sodium, potassium, total cholesterol, neutral fat, CK (CPK)
Haematology test:	Red blood cell count, hemoglobin, hematocrit, white blood cell count, leukocyte differential count (neutrophil, eosinophil, basophil, lymphocyte, monocyte), platelet count
Urinalysis (qualitative)*:	Occult blood, protein, glucose

* About 10 mL of urine is collected and tested by the test paper method.

4.7.2.2 Methods of assessment

During the study period, [REDACTED] will be designated as a central laboratory for this study in order to assure that the standardisation of the assessment and clinically significant comparison between the 3 treatment groups will be accomplished.

Clinical laboratory tests at Visit 1 must be conducted at the central laboratory for all subjects who provided informed consent within 1 week prior to randomisation. The investigator(s) may confirm the eligibility of the subjects based on the results of tests performed the study centre within 2 week prior to randomisation, even if the test values were collected before provision of informed consent. However, baseline clinical laboratory tests must be conducted at the central laboratory within 1 week prior to randomisation.

If the investigator(s) considers it clinically necessary (eg, in the case of abnormal or severe adverse event), additional blood samples may be taken.

For the blood samples measured by [REDACTED], the central laboratory will supply the materials (eg, test tubes, labels) necessary for collection of the blood samples, storage, and transfer. Methods of collection of the blood sample, processing, and transfer are described in the manual that will be provided to each study centre.

See Section 4.7.1.2 for details of methods for recording and reporting AEs based on the findings of clinical laboratory values.

4.7.3 Vital signs and physical examination

(a) Vital signs

At all visits except for Visit 2, blood pressure/pulse rate will be measured in a sitting position.

(b) Physical examinations

At all visits, general appearance, lymph node, thyroid gland, cardiovascular system, lung, abdomen, musculoskeletal/extremities, and reflex will be examined. Presence/absence of deterioration or new findings from the baseline (Visit 2) will be checked, and if relevant findings are found, they will be recorded as AEs in the eCRF.

4.8 Volume of blood sampling and handling of biological samples

The total volume of blood that will be drawn from each subject in this study is as follows:

Table 8 Volume of blood to be drawn from each subject

Assessment		Sample volume (mL)	No. of samples	Total volume (mL)
Characteristic of patient	Hp test	2	1	2
Safety	Biochemistry	4	3	12
	Haematology	2	3	6
Genotyping	CYP2C19	2	1	2
Total				22

4.8.1 Analysis of biological samples

4.8.1.1 Biochemistry samples

The analyte stability limits defined by [REDACTED] will be applied to all analyses performed on behalf of AstraZeneca KK. [REDACTED] will not analyse samples that fall outside these stability limits. The results will not be reported if found to have been derived from a sample that fell outside these stability limits. The standards of procedure followed by [REDACTED] may be amended in accordance with its Standard Operating Procedures.

If [REDACTED] chooses to sub-contract the analytical work to another laboratory, [REDACTED] must assure itself and provide assurance to AstraZeneca KK that the other laboratory will apply defined stability limits to all analyses performed on behalf of AstraZeneca KK. Samples falling outside these limits must not be analysed or data reported.

4.9 Genetic test

4.9.1 Purpose of genetic test

The purpose of the genetic research is to investigate the genotype of CYP2C19, a metabolising enzyme of D961H known to have two genotypes, namely 'EM' (homo- and hetero-types) and 'poor metaboliser (PM)'. Since the changes in the blood D961H concentrations showed different tendency between the two metabolisers and the difference is considered to affect the efficacy of D961H, they will be examined (see [REDACTED] for criteria for evaluation of phenotypes).

4.9.2 Collection of samples for genetic research

Subjects will provide a blood sample of 2 mL at screening to be used for genetic test of cytochrome P450 subtype CYP2C19, a metabolising enzyme of D961H.

[REDACTED] will carry out collection of the samples and measurement.

Genotype is a stable parameter, therefore if for any reason the blood sample is not drawn at screening, it may be taken at any visit until the discontinuation or completion of the study. It is preferable that the blood sample for genotype will be collected at the same time when blood samples for other assessment are collected.

Procedures for sample collection and shipment must be followed as described in [REDACTED]

4.9.3 Storage and coding of samples for genetic test

Special attention is required for conducting a genetic test. The following items should be obeyed to conduct a genetic test and explained to the subjects at the time informed consent is provided:

- Written informed consent to a genetic test must be provided by each subject.
- From the aspect of this study design, implementation of a genetic test is a requirement for the subject to participate in the study.
- From the aspect of this study design, personnel involved in the study at the study centres and AstraZeneca KK will have knowledge of genetic information on the subjects based on the genetic test results.
- Samples for the genetic test to be sent to the laboratory will not be labelled with subject identifiers so that the information on the subject will not be revealed to any other parties.
- Samples of the subject who is not enrolled in the study will be destroyed immediately by the study site on [REDACTED].

- If the genetic test for the sample of the subject who is not enrolled in the study was completed, the results of the test and the records will be destroyed immediately by [REDACTED].
- In the case the subject in concern wishes a release of the genetic test results in the informed consent form, the result will be disclosed to the subject via investigator(s) after the database of the following study (D961HC00006) is locked. However, the result will be disclosed to the subject immediately even before the database is locked only when the subject requests to do so during the study period.
- All samples collected for a genetic test will be used only for CYP2C19 genotyping and will be destroyed immediately by [REDACTED] after completion of the genetic test on CYP2C19.

5. DATA MANAGEMENT

Data will be entered in the WBDC system at the study site. Trained study personnel will be responsible for entering data on the observations, tests and assessments specified in the protocol into the WBDC system and according to the eCRF Instructions. The eCRF Instructions will also provide the study site with data entry instructions. Data entered in the WBDC system will be immediately saved to a central database and changes tracked to provide an audit trail. AstraZeneca KK will make an inquiry to the investigator(s) for missing, unreal, or conflict data that have been entered using the WBDC system. When data have been entered, reviewed and edited, and Source Data Verification performed, the principal investigator will be notified to sign the eCRF electronically as per the agreed project process and data will be locked to prevent further editing. A copy of the eCRF will be archived at the study site. Quality control procedures will be applied to each stage of the data handling to ensure that all data are reliable and have been processed correctly.

6. STATISTICAL METHODS AND DETERMINATION OF SAMPLE SIZE

6.1 Statistical evaluation – general aspects

A comprehensive Statistical Analysis Plan will be prepared before unblinding of the data. A significant level of $p < 0.05$ (two-sided) will be used, in principle, for statistical tests and interval estimation.

All statistical analyses in this study will be performed by Statistics and Programming Department of AstraZeneca KK using the SAS software.

6.2 Description of outcome variables in relation to objectives and hypotheses

6.2.1 Primary outcome variables

The primary variable of this study is the presence/absence of RE at Week 8 according to LA classification.

6.2.2 Secondary outcome variables

The secondary outcome variables of this study are as follows.

Efficacy

- Presence/absence of RE at Week 4 according to LA classification.
- Time to sustained resolution of each GERD symptom (definition: number of days from the starting day of investigational product administration up to the first day of 7 consecutive days free of that symptom).
- Time to sustained resolution of all GERD symptoms (definition: number of days from the starting day of investigational product administration up to the first day of 7 consecutive days free of all symptoms).
- The proportion of subjects without each GERD symptom during the 7 days preceding visits at Week 1, 2, 4 and 8.
- The proportion of subjects without each GERD symptom or with 'Mild' GERD symptoms up to 1 day during the 7 days preceding visit at Week 1, 2, 4 and 8.
- QOLRAD

Safety

- AEs
- Laboratory test values
- Vital signs (blood pressure and pulse rate)

6.3 Description of analysis sets

For the efficacy data analysis, two analysis sets, that is, the full analysis set (FAS) and per protocol set (PPS) will be used. The FAS will be used as the primary efficacy analysis set. Both FAS and PPS will be used for the analysis of the primary variable but only FAS will be used in the analysis of secondary efficacy variables.

All the randomised subjects who are definitely diagnosed to have RE by the EGD before the start of administration and who have taken at least one dose of investigational product will be included in the FAS. Of the subjects included in the FAS, those who have no major protocol violations or deviations that may affect the efficacy assessment and those who have a good compliance with the study will be included in the PPS. The population excluding subjects who are declared not to have RE by the central evaluation committee (see Section 6.7) before dosing will be also evaluated. In this analysis, the evaluation of the central evaluation committee for the healing of RE after dosing will be used.

All the analysis sets will be determined before unblinding of the data.

All the subjects who have taken at least one dose of investigational product and whose data after the treatment start are available will be included in the safety analysis set. All the safety analyses will be conducted using the safety analysis set.

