3. STUDY PLAN AND PROCEDURES

3.1 Overall study design and flow chart

This Clinical Study Protocol has been subjected to a peer review according to AstraZeneca standard procedures.

This is a multicentre, randomised, double-blind, double dummy, parallel-three group study to evaluate the efficacy and safety of D20, D40 and O20 in patients with RE.

The subjects with RE endoscopically verified grade A, B, C or D by LA classification at the time of screening, that is, within 1 week prior to initiation of the investigational product administration, will be classified based on the LA classification in grade A/B and C/D, and will be randomised to D20 group, D40 group or O20 group at the ratio of 1:1:1 in each group.

Esophagogastroduodenoscopy (EGD) will be done at Week 4 and 8 to find whether RE is healed or not. If the healing is observed at Week 4 in a subject, the subject will complete the study at the time point. The maximum duration of investigational product administration

period is 8 weeks. In addition to checking the safety throughout the study period (from the day of informed consent to the day of the last scheduled visit or withdrawal), the GERD symptoms are assessed by subjects themselves using the patient diary. Furthermore, HRQOL is assessed using QOLRAD.

A patient whose RE is healed in this study may be enrolled in the follow-on clinical study (D961HC00006) in which the efficacy and safety of D961H will be assessed on the maintenance of healed RE after the informed consent and the eligibility assessment.

All EGD images of all patients allocated the investigational products during the study period will be reviewed by the central evaluation committee (see Section 6.7) established by AstraZeneca K.K. under the blinded conditions as needed.

Figure 1 and Table 1 present the study flow chart and the schedule of the study.

Figure 1 Study flow chart

[figure not shown]

Table 1 Study plan

	Screening		Study Treatment	
		Randomisation		
Visit	1	2	3 Week 4	4 (or at discontinuation) Week 8
Days after Visit 2	-7 to 0	0	28	56
Time window (days)	-	-	±4	±4
Informed consent ¹⁾	X			
Inclusion/exclusion criteria	X	X		
Demographic data	X			
Medical/surgical history	X			
Underlying diseases	X	X		
Physical examination	X	X	X	X
Vital signs	X		X	X
Clinical laboratory tests ²⁾	X		X	X
Pregnancy test (urine) ³⁾	X			
Hp test (IgG antibody)	X ⁶⁾			
Genetic test for CYP2C19	X ⁶⁾			
QOLRAD (HRQOL)		X	X ⁸⁾	X ⁸⁾
EGD ⁴⁾	X ⁷⁾		X ⁹⁾	X
Randomisation		X		

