Dispense Patient Diary		X	X	
Review/Collect Patient Diary			X	X
Dispense investigational products		X	X	
Review/Collect returned investigational products			X	X
Review treatment compliance			X	X
Check concomitant medications	←			→
AEs ⁵⁾	←			→

1) Within 3 weeks (21 days) before visit 2 (randomisation).

2) Central laboratory is used for laboratory tests. If the results of test conducted within 2 weeks before randomisation at the laboratory test department of each participating medical institution are available, the

eligibility may be checked using these test values even if obtained before the informed consent. However, the baseline laboratory test values should be determined within 1 week before randomisation at the central laboratory.

- 3) Conducted in pre-menopausal females with a child-bearing potential.
- 4) Conducted in fasting condition.
- 5) As to serious adverse events (SAEs) and AEs resulting in discontinuation, all those that occur after informed consent are recorded in the electronic case report form (eCRF). As to the AEs other than serious or resulting in discontinuation, those that occur from the start of investigational product administration to the day of the last scheduled visit or withdrawal are recorded in eCRF.
- 6) If it is not possible to conduct it at the time of screening, the test may be conducted at any visit during the treatment period until the discontinuation or completion of this study.
- 7) If the results of test conducted within 1 week before randomisation are available, these data may be used with the consent of subject even if obtained before informed consent.
- 8) The subject fills in QOLRAD after receiving EGD.
- 9) When the healing of RE is verified by EGD, this study is completed.

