4.6.1.2 Method of assessment

When no breaks in the esophageal mucosa are found by EGD, the RE will be judged as "healed". When healing of RE is verified on Visit 3, the subject will complete the study at the time point.

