6.4 Method of statistical analysis

6.4.1 Primary outcome variables

The proportion of subjects with healed RE verified at Visits 3 or 4 in the analysis set is defined as the healing rate at Week 8.

The healing rate of RE at Week 8 and its two-sided 95% confidence interval will be calculated for each group. The difference in healing rates between the D40 group and O20 group (D40 group – O20 group) and between the D20 group and O20 group (D20 group – O20 group) along with the two-sided 95% confidence intervals will be obtained. It is concluded that the non-inferiority of D40 to O20 is verified if the lower limit of the two-sided 95% confidence interval of the difference between D40 group and O20 group exceeds -10%. If the non-inferiority of D40 to O20 is verified, the verification of the non-inferiority of D20 to O20 will be investigated similarly.

The healing rate at Week 8 will be compared between D40 group and O20 group and between D20 group and O20 group using Cochran-Mantel-Haenszel test stratified by baseline LA classification or CYP2C19 genotype. In these comparisons, the significant level will not be adjusted.

The healing rate at Week 8 in each subgroup and its two-sided 95% confidence interval will be calculated by dose group regarding the following factors.

- Sex
- Age (<65 years old, ≥65 years old)
- Presence or absence of Hp infection
- CYP2C19 genotype (homo EM, hetero EM, PM)

- Baseline LA classification (grade A/B, grade C/D)

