6.6 Interim analyses (Not applicable)

6.7 Central evaluation committee

For this study, a central evaluation committee that consists of experts in the gastrointestinal area will be established to confirm the rationale for judgement by the investigator(s) based on the EGD images.

The board will review all EGD images of all patients allocated the investigational products during the study period as needed and report the results of the review to AstraZeneca K.K..

Time to hold the meeting and the responsibilities of the board members will be determined separately.

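### In the supplementary committee-read analysis, a subject who left at Visit 3 on a site reading of healed, but whom the committee reads as unhealed, counts as a Week 8 failure with no Week 8 endoscopy

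*Protocol*

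**What the plan says.** - **Exit at Visit 3.** Section 3.1: "If the healing is observed at Week 4 in a subject, the subject will complete the study at the time point". Section 4.6.1.2 repeats the rule: "When healing of RE is verified on Visit 3, the subject will complete the study at the time point". Footnote 9 to Table 1 says the same: "When the healing of RE is verified by EGD, this study is completed". None of the three makes exit wait for a central reading.
- **Role and timing of the committee.** Section 6.7 sets the committee up "to confirm the rationale for judgement by the investigator(s) based on the EGD images". On extent it says "The board will review all EGD images of all patients allocated the investigational products during the study period as needed", and on timing "Time to hold the meeting and the responsibilities of the board members will be determined separately".
- **The supplementary analysis.** Section 6.3 makes the FAS the primary efficacy set and uses the PPS as well for the primary variable. It then adds an evaluation of a population without the subjects whom the committee finds not to have had esophagitis before dosing. For that evaluation, "In this analysis, the evaluation of the central evaluation committee for the healing of RE after dosing will be used".
- **The endpoint.** Section 6.4.1 takes as the Week 8 healing rate "The proportion of subjects with healed RE verified at Visits 3 or 4 in the analysis set", so the denominator is everyone in the set.

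**The concern.** The site's reading decides who receives a second month of treatment and a Visit 4 endoscopy. The supplementary analysis then scores healing by a different reader. Where the site says healed at Visit 3 and the committee says unhealed, the committee-read status at Week 8 was never observed, yet the endpoint definition scores it as failure. The opposite disagreement has no such effect: a subject whom the site calls unhealed and the committee healed stays on treatment, is examined again, and still counts as healed at Visit 3.

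This matters because the primary endpoint is read by investigators at about 70 centres (synopsis), each using its usual endoscopy method (section 4.6.1.1). The committee-read analysis is the only efficacy analysis in the protocol that changes the reader. If its Week 8 rate includes unobserved outcomes scored as failures, agreement or disagreement with the primary result is hard to interpret. The missing endoscopy cannot be recovered: healed subjects may enter the maintenance study D961HC00006 (section 3.1), where a later examination would not reflect the assigned 8-week course.

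**Working it through.** **1. What the rules give for each pair of Visit 3 readings**

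| Site | Committee | Visit 4 endoscopy | Committee-read Week 8 status under 6.4.1 |
|---|---|---|---|
| healed | healed | no | healed |
| healed | unhealed | no | non-healed, though Week 8 was not observed |
| unhealed | healed | yes | healed |
| unhealed | unhealed | yes | decided by the committee's Visit 4 reading |

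Only the second row is scored on an outcome that nobody could see.

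**2. The plan's own figures, for scale.** Section 6.5 assumes 85% (D20) and 82% (O20), a 10-point margin and a two-sided 95% interval.
- n = (1.960 + 1.282)² × (0.85×0.15 + 0.82×0.18) / 0.13² = 10.51 × 0.2751 / 0.0169, which rounds up to 172, as stated.
- At 185 per arm, SE = √(0.2751/185) = 3.9 points, and non-inferiority power is 92.1%.

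**3. How many subjects could be involved.** The protocol gives neither the site-read Week 4 healing rate (h4) nor the share d of those subjects whom the committee would overturn. Assume h4 of 60 to 80% and d of 5 to 20%.
- Low end: 185 × 0.60 × 0.05 ≈ 6 subjects per arm, or 3 points of the Week 8 rate.
- High end: 185 × 0.80 × 0.20 ≈ 30 subjects per arm, or 16 points.

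**4. Direction of the shift.** Take the plan's Week 8 rates (85%, 82%; true difference +3) and assumed Week 4 rates of 70% (D20) and 60% (O20).

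*Model A.* A fixed share f of truly unhealed Week 4 subjects is read as healed by the site, and the committee is right. Healings lost = (1 − p4) × f × (p8 − p4)/(1 − p4) = f × (p8 − p4).
- f = 10%: D20 loses 0.10 × 15 = 1.5 and O20 loses 0.10 × 22 = 2.2. The difference becomes 3 + 0.7 = **+3.7**.
- f = 20%: D20 loses 3.0 and O20 loses 4.4. The difference becomes 3 + 1.4 = **+4.4**.

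*Model B.* The committee overturns a fixed share d of site-healed Visit 3 subjects. Reduction from the assumed Week 8 rate = d × h4.
- d = 5%: D20 loses 3.5 and O20 loses 3.0. The difference becomes 3 − 0.5 = **+2.5**.
- d = 20%: D20 loses 14 and O20 loses 12. The difference becomes 3 − 2 = **+1.0**.

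Model A measures the departure from what the committee would have read after a full course. Model B measures the departure from the assumed Week 8 rate. Model A helps the arm that heals faster and Model B penalises it. The protocol contains nothing that would choose between them.

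**5. Against sampling error.** The shifts are 0.7 to 1.4 points under A, or 0.2 to 0.4 of the 3.9-point SE, and 0.5 to 2.0 points under B, or 0.1 to 0.5 of it. Under B, non-inferiority power in this analysis, Φ((difference + 0.10)/SE − 1.96) with the SE recomputed at the reduced rates, falls from 92.1% to 85.6% (d = 5%) or 64.1% (d = 20%).

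**The case against.** **This belongs in the SAP.** Section 6.1 promises one before unblinding, and the handling of unobserved readings in a supplementary analysis is commonly settled there. This stands as to where the fix may go. It does not remove the point, because the protocol already fixes the exit rule, the reader and the endpoint, and it is these three together that misclassify the subjects.

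**Failure status and timing are inferred.** This is correct. Section 6.3 does not restate the endpoint, so the failure status comes from joining it to section 6.4.1. Section 6.7 leaves the meeting dates open. But no passage places a central reading before exit, so the sequence is not prevented.

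**The committee is not the truth.** It reads submitted images, while the site performs the endoscopy. A wrong committee reading of healed at Visit 3 also counts as healed whatever Visit 4 shows, which is an upward error. So it cannot be said that all error in this analysis runs one way. What runs one way is the loss of treatment and follow-up.

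**Mixing 4- and 8-week courses is not special to this analysis.** True: section 6.4.1 defines healing cumulatively in every set. The particular problem is scoring an unobserved outcome as a failure.

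**Stronger readings.** A reader might infer that the primary non-inferiority conclusion is biased. The protocol does not support this, since the FAS analysis is not described as using committee readings. A reader might also infer that the distortion favours the faster-healing arm. That holds under one error model and reverses under another.

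**Conclusion.** The point holds for the supplementary committee-read analysis only. In that analysis, subjects read as healed by the site and unhealed by the committee at Visit 3 are counted as Week 8 non-healers after about 4 weeks of treatment and without a Week 8 endoscopy. This rests on two inferences: that the section 6.4.1 definition carries over to the section 6.3 analysis, and that the central reading does not come before exit.

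The size is unknown. The 6 to 30 subjects per arm and the shifts in the difference depend entirely on assumed Week 4 rates and disagreement rates. They also take 185 per arm, although the committee's baseline exclusions would make this population somewhat smaller. The sign of any between-arm shift is undetermined. This is a cheap improvement to a secondary check and no defect in the primary test.

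**What to change.** In section 6.3, or in the SAP before unblinding:

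1. State that committee-read Week 8 status is unobserved for subjects who left at Visit 3 on a site reading of healed and whom the committee reads as unhealed.
2. Report their number in each arm.
3. Give each D961H-O20 difference with its 95% confidence interval under four assumptions: all such subjects healed, none healed, and the two opposing worst cases (healed in one arm only).
4. Report committee-read Week 4 healing as the directly comparable check, since early exit does not affect it.
5. Optionally add a life-table estimate that censors these subjects at Visit 3, as a further sensitivity analysis only. The censoring may be informative, because subjects on whom the readers disagreed need not heal like those who continued as clearly unhealed.

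The exit rule itself need not change. The cost is a paragraph and a few tables, with no new visits, data or readers. The drawback is that the committee result becomes a range. The gap between the opposing worst cases is the sum of the two arms' discordant shares: 3 + 3 = 6 points at d = 5% with h4 = 60% in both arms, and 14 + 12 = 26 points at d = 20% with h4 of 70% and 60%. A wide range would itself show how little this check can say about Week 8.
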